1.3 Intended use of Investigational Device

The ONT GridION MK1 Sequencing Instrument (Device number GXB03025) will be used in conjunction with an optimized phenol chloroform DNA extraction to perform metagenomic sequencing on DNA extracted from intraoperative bile aspirate samples taken from patients undergoing total pancreatectomy and pancreaticoduodenectomy. The technology will utilize ONT sequencing and the data output will be basecalled read sequences in the fastq file format. Sequenced reads will be analyzed for microbial identification and AMR prediction.

1.4 Clinical Data to Date

This study will use data that has been collected under the following research study: "Comparative Analysis of Bile Microorganisms in Patients Undergoing Major Hepatobiliary Operations", IRB# 19-011419 and published in two peer-reviewed journals^{44,48}. In brief, these studies involved analysis of intraoperative bile aspirate samples collected from 42 patients undergoing pancreatic head resection (total pancreatectomy, n = 9; pancreaticoduodenectomy, n = 33) at Mayo Clinic, Rochester (see Table 1 for patient characteristics). Metagenomic ONT sequencing was performed on bile aspirates to identify microbial species (bacterial, fungal) and antibiotic resistance genes. Sequencing results were then compared to bile cultures performed as part of Mayo Clinic's standard of care clinical practice to determine how ONT sequencing compared to current 'Gold Standard' culture practices^{44,48}.

To determine the optimum ONT protocol for detection of microbial species and antibiotic resistance genes present in the bile aspirates, different methods of DNA extraction, use of host DNA depletion, and use of different AMR gene databases were evaluated⁴⁸. In total, intraoperative biliary microbes were detected in 54.7% (23/42) of patients undergoing total pancreatectomy or pancreaticoduodenectomy using SC techniques. This included 35.7% (15/42) of patients with positive bacterial cultures, 2.4% (1/42) of patients with positive fungal cultures, and 16.7% of patients with positive fungal and bacterial cultures. The male sex, use of biliary instrumentation, and performance of vascular reconstruction during surgery was significantly correlated with the detection of biliary microbes.

Table 1: Clinical characteristics of patients included in our preliminary study

Clinical feature	Total	Biliary microbes ⁺	Biliary microbes ⁻	P value
Age, mean (IQR)	61 (22 - 71)	66.3 (46.3 - 81.3)	58.0 (18 - 82.6)	0.0858
BMI, mean (IQR)	26.4 (19 - 40.4)	26.3 (19 - 40.4)	26.4 (19.7 - 36.2)	0.9295
Sex, % male (n)	54.8 (23)	38.1 (16)	16.7 (7)	0.0375
Surgery indication, % (n)				0.892
Pancreatic ductal adenocarcinoma	45 (29)	50 (21)	19.0 (8)	
Intraductal Papillary Mucinous Neoplasm	7.1 (3)	0 (0)	7.1 (3)	
Neuroendocrine tumors	11.9 (5)	2.4 (1)	9.5 (4)	
Other	11.9 (5)	2.4 (1)	9.5 (4)	
ASM Score, mean (IQR)	2.6 (1 - 4)	2.7 (2 - 4)	2.5 (1 - 3)	0.1874
Type of surgery				0.9716
Total pancreatectomy, % (n)	21 (9)	11.9 (5)	9.5 (4)	
Pancreaticoduodenectomy, % (n)	79 (33)	42.9 (18)	35.7 (15)	
Biliary instrumentation, % (n)	52 (22)	52.4 (22)	0 (0)	<0.0001
Vascular reconstruction, % (n)	38 (16)	31.0 (13)	7.1 (3)	0.0079

BMI, body mass index; IQR, interquartile range

Comparison of our optimized ONT sequencing protocol SC results revealed that our ONT protocol had identified 100% of biliary microbial contamination cases, detected 75% of cultured bacterial species and 76% of cultured fungal species, and predicted 81% of antibiotic resistance phenotypes observed using SC results ^{44,48}. With regards to detection of common biliary pathogens ^{3,54-57}, our ONT protocol improved detection of biliary candidiasis, detected 100% of cases of biliary *Escherichia coli* and biliary *Klebsiella*, and detected 83% of biliary *Enterobacter*, 76.5% of biliary *Enterococcus*, 93.8% of biliary *Streptococcus*. However, ONT did not detect one case of *Pseudomonas* infection and one case of *Staphylococcus aureus*, indicating as proposed in this study that SC techniques should be run alongside ONT protocols to ensure that no microbial species are missed. As for detection of pathogens of high clinical concern (i.e. ESBL, CRE species), ONT similar detection rates compared to SC, and potentially improved detection of *E. coli*, *K. oxytoca*, *K. pneumoniae*, and *Citrobacter freundii*. Overall, ONT improved detection of microbial species (particularly with regards to anaerobic species and fungal species) and predicted a significantly higher number of antibiotic resistance phenotypes than were identified using SC. Significantly, the results turnaround for ONT sequencing was just 14 hours compared to an average turnaround time of 98 hours for SC. On average, it took 4.8 days (range = 1 – 15 days) to complete microbial identification and an additional 2 days (range = 0 – 9 days) to complete AST for the culture positive samples. Delays greater than 5 days in completing microbial identification occurred in samples with multiple aerobic species of the same genus (*Enterococcus* spp., *Klebsiella* spp., *Streptococcus* spp.), anaerobic species (*Schaalia (Actinomyces) turicensis*, *Finegoldia magna*, *Veillonella* sp., *Actinomyces johnsonii*, *Parvimonas micra*), and/ or fungal species *Saccharomyces cerevisiae*, *Candida* spp.), and on average, optimal antimicrobial therapy was delayed for 7 days. Use of a test that would enable microbial identification and prediction of AMR phenotypes within 24hrs post-surgery, would, therefore, have significantly shortened the delay in patients receiving optimized tailored antimicrobial therapy post-surgery.

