fashion would be highly advantageous. It would allow for all the microbial information to be generated in a single report, enabling the administration of optimal tailored antibiotics in the early postoperative window without the need for continuous changes to the treatment regimen as new information becomes available. It would also enable early cessation of antimicrobial prophylaxis if no microbes are detected, potentially reducing the complications associated with use of broad-spectrum antibiotics.

We hypothesized that use of metagenomic Oxford Nanopore (ONT) sequencing, a real-time method of sequencing that has been demonstrated to detect microbial species in as little as 6 hours^{42,46,47}, could be developed as a tool for rapid detection and characterization of biliary microbes. We have since developed methods of detecting intraoperative bile microbes, and have recently published the promising results of a prospective clinical trial that was performed to determine the feasibility and utility of ONT sequencing in detection of microbial species and antibiotic resistance genes using intra-operative bile from patients undergoing pancreatic head resection^{44,48}. Our preliminary data would suggest that not only is this technique feasible, but our ONT sequencing results highly correlate with traditional culture microbial identification and does so with a median time of 14 hours compared to 98 hours for traditional culture, a turnaround time improvement of 92%. Furthermore, the results of our study found that when standard cultures (SC) were negative (i.e. no further antibiotic therapy needed) the ONT perfectly correlated. This suggested that ONT could be used to identify patients with negative biliary microbes, enabling a more rapid cessation of unnecessary antimicrobial therapy in patients. This would improve antibiotic stewardship, a continual goal in surgical patient care.

Given these promising preliminary results, we aim to reduce the rate of SSI while minimizing overutilization of antibiotic therapy in patients undergoing pancreatic head resection by providing supplemental ONT data in addition to standard clinical cultures. This will provide not only an important potential diagnostic, but will also elucidate microbial communities within contaminated bile, potentially leading to improved targeted approaches in the future.

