ONT results different from SC	Adjust and/or narrow antibiotic therapy to cover pathogens found in ONT results, excluding those deemed clinically insignificant. SC results to only be considered in the event of treatment failure with antibiotic therapy targeted towards ONT results.

Databases Used

For the analysis of our endpoints, we are relying on sequence homology for two main tasks, mainly, (1) the identification of species and (2) identification of AMR phenotypes. For species identification, we use the refseq genome database (downloaded on 12/18/2020) with all data from the following higher order taxa groups included: human, protozoa, viral, bacterial, and fungal. For the identification of AMR phenotypes, we use the ResFinder database (downloaded on 06/04/2021, version 4.1) which contains the acquired chromosomal resistance genes, ensuring we know which species is carrying a given resistance gene. For plasmid AMR gene identification, we will use the PlasmidFinder-specific database (downloaded on 7.14.2021/version 2.0.1) and the CARD data (downloaded on 07/07/21, version CARD 2020). These databases undergo regular updates since they were first developed. To ensure the analysis remains consistent throughout the study, databases will not be updated for the duration of the study. In the unlikely event that we require a software/ database update in order to run these tools (compatibility issues with future institutionally required OS update, inability to restore databases from archives after computational disaster), we will validate any newer versions of the database and/or algorithms using the data and culture gold standards from our published study and recently collected data and will only proceed if we have comparable performance in accuracy for species and AMR identification.

Patient Follow-up and Safety Monitoring

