6.1 Sample Size Determination

Data for power analysis based on pilot study data (IRB# 19-011419). Power analysis is based on improvement in antibiotic stewardship with the following assumptions:

- Treatment groups are random and independent
- Microbial detection positivity rate using standard cultures = 54%
- Microbial detection positivity rate using nanopore sequencing = 77%

Analytical method:

- Sample size per group = 66 (total N = 132), Target size=70 per arm, total N=140
- Power = 80%, alpha (type I error) = 0.05, beta (type II error) = 0.2

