6.2 Statistical Methods

Descriptive Statistics

The primary analysis of this study will be a modified intention to treat analysis (ITT), performed to determine how use of ONT changed patient treatment, i.e. did use of ONT improve antibiotic stewardship. Proportions of patients with detection of microbes of interest will be estimated along with exact 95% binomial confidence intervals. Comparisons of the proportions between the two study arms will be compared using Fisher's exact test or Chi-square test as appropriate. We will calculate the time from randomization to first microbial detection within a patient. We will report the mean difference in time to first microbial detection within 96 hours post randomization in both treatment arms, together with a 95% confidence interval. Comparison of time to first microbial detection within 96 hours post randomization, will be performed using Wilcoxon rank sum test or two sample t-test as appropriate. If there are any baseline imbalances in demographic or clinical variables between the two groups, we will perform the analysis using univariable and multivariable linear regression adjusting for these variables with imbalances as possible confounders. Duration of antibiotics, total number of different antibiotics, and broad-spectrum antibiotics vs narrow-spectrum antibiotics administered in the two arms will be compared to determine if use of ONT improved antibiotic stewardship by significantly reducing the duration of perioperative antibiotics and use of broad-spectrum antibiotics

Secondary analysis will evaluate SSI's will be evaluated and classified using ACS NSQIP definitions and data collected will include mortality rate, SSI incidence rate, ICU length of stay, total length of hospital stay, need for interventional procedures, and hospital readmission. Statistical analysis will be performed by the study team to determine if use of ONT significantly improved patient outcome compared to patients who received standard of care

only. The secondary endpoint of the study is a binary endpoint i.e. whether patients develop SSI (yes, no). Association between the secondary outcome and predictor variables will be assessed using univariable and multivariable logistic regression.

In both primary and secondary analysis, the following variables will be assessed for inclusion in the regression models

- Age at time of surgery DOB
- BMI at time of surgery RAVE calculate
- Sex

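### The between-arm detection comparison on which the trial is sized has no reference standard, so it cannot separate better detection from over-calling by sequencing

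*Combined protocol and SAP*

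**What the plan says.** Section 6.1 introduces the sample size with "Power analysis is based on improvement in antibiotic stewardship with the following assumptions" and then gives two rates, both in per cent: "Microbial detection positivity rate using standard cultures = 54" and "Microbial detection positivity rate using nanopore sequencing = 77". With alpha 0.05 and 80% power it reports 66 per group and a target of 70 per arm.

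Section 6.2, in the paragraph that opens with the primary analysis, states: "Proportions of patients with detection of microbes of interest will be estimated along with exact 95% binomial confidence intervals". The proportions are then compared between arms by Fisher's exact or chi-square test. The section does not define which organisms count. It does not say whether culture, ONT or either defines detection in Arm 2, where both are run. It gives no agreement or specificity measure.

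Elsewhere culture is the reference. Section 1.4 compares ONT with culture as the gold standard, and the database paragraph of 2.1 General Design would validate any software or database update "using the data and culture gold standards from our published study".

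On pilot accuracy, 1.1 reports that "when standard cultures (SC) were negative (i.e. no further antibiotic therapy needed) the ONT perfectly correlated", and 1.4 says that ONT identified all contaminated cases, with culture positive in 23 of 42 patients. Section 1.4 also concludes: "Overall, ONT improved detection of microbial species (particularly with regards to anaerobic species and fungal species".

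The success criteria (2.2 Primary Objective) and the primary endpoint (2.2 Primary Study Endpoints) concern antibiotic use. Section 5.3 says that culture and ONT results will be captured and compared, without a method.

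**The concern.** A higher positive rate in the ONT arm can arise in two ways: ONT finds organisms that are present and culture misses, or it reports organisms that are absent or irrelevant. A between-arm test of proportions treats both alike. Nothing in it lets a false positive count against ONT. A paired superiority test would have the same fault, because the difficulty is the direction of scoring and not the pairing.

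The label in 6.1 adds to this. Under 2.1 General Design, a negative ONT result leads to early discontinuation. A patient called positive generally leaves that route unless the organisms are judged clinically insignificant. More positives can therefore run against the stewardship aim that the 54% v 77% gap is said to represent.

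At stake is the claim the trial can make. A significant excess of ONT positives could be reported as improved detection, or as support for improved stewardship, when the excess is unconfirmed by the documents' own reference.

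**Working it through.** **Inputs.** Culture positivity 54%, ONT positivity 77%, alpha 0.05, power 80%, 66 calculated and 70 targeted per arm (6.1); 1:1 allocation (5.2); pilot culture positivity 23/42 and all cases found by ONT (1.4); perfect agreement when culture was negative (1.1).

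**Step 1: reproduce the plan's figure.** Two proportions, two-sided, pooled variance under the null, no continuity correction:

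n = [1.960·√(2·0.655·0.345) + 0.842·√(0.54·0.46 + 0.77·0.23)]² / 0.23² = (1.318 + 0.549)² / 0.0529 ≈ 65.9, that is 66 per arm.

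This matches 6.1, so the sizing comparison is a simple between-arm difference in positivity. Power at 70 per arm is 82.4%.

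**Step 2: what the pilot statements imply.** If ONT finds every culture-positive patient and agrees on every culture-negative one, ONT positivity equals culture positivity: 23/42 = 54.8%. To reach 77% with no culture-positive patient missed, the share of culture-negative patients called positive must be

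(0.77 − 0.54) / 0.46 = 50%, or (0.77 − 0.548) / (19/42) = 49% from the pilot counts.

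So the whole planned gap consists of ONT-positive, culture-negative patients, a group that 1.1 and 1.4 together say was empty in the pilot.

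**Step 3: how the test responds to over-calling.** Suppose ONT finds every culture-positive patient and over-calls a share f of culture-negative bile. ONT positivity is then 0.54 + 0.46f. Chance of a two-sided 0.05 result favouring ONT at 70 per arm:

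| f (assumed) | ONT positivity | Chi-square (normal approximation) | Fisher (enumerated) |
|---|---|---|---|
| 10% | 58.6% | 7.9% | 6% |
| 20% | 63.2% | 19.5% | 15% |
| 30% | 67.8% | 38.6% | 32% |
| 40% | 72.4% | 61.9% | 55% |
| 50% | 77.0% | 82.4% | 78% |

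Exact enumeration of the chi-square test at f = 50% gives 82.7%.

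**Step 4: sensitivity to missed patients.** At f = 50%, if ONT alone defines detection and finds 90% of culture-positive patients, positivity is 0.9·0.54 + 0.23 = 71.6% and the chi-square figure falls to 57.8%. At 80% it is 66.2% and 31.2%. If either test counts as detection in Arm 2, missed patients no longer lower the rate, and the Step 3 table applies whatever ONT's sensitivity.

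**The case against.** Five points on the other side carry weight.

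- **No success rule rests on detection.** A reader might infer that an over-calling test would make the trial succeed about 82% of the time. The documents do not support that. Success is defined on antibiotic duration and broad-spectrum use, and over-calling would tend to work against those. The figures apply to the detection comparison alone, which 6.2 places under a descriptive heading although inside the primary-analysis paragraph.
- **The 82% is the planned power under another name.** f = 50% is the value that returns 77%, and no document gives an over-call rate. The perfect agreement reported in 1.1 points to f near zero, where the figures are small. The table is an illustration and not a forecast.
- **Some ONT-only calls may be real.** The plan argues that culture is slow or weak for anaerobes and fungi, and antibiotics given before incision could suppress growth in culture. The 500-read rule, the reads-per-million ratio against a negative control and the 1% abundance cut-off (2.1 General Design), with a new flow cell for each patient (4.5), also limit contamination calls. These safeguards reduce false calls, but the analysis still cannot tell true extras from false ones.
- **Table 2 does not measure false positives.** A reader might point to the high-concern list, where 13 of 35 ONT calls (37%) lack culture confirmation. The common-pathogen list gives 12 of 64 (19%). Both count species, and an extra species in an already positive patient does not change patient-level positivity. Two Klebsiella species in one patient are not evidence of error either; 1.4 itself describes samples with several species of that genus.
- **Speed could also produce a difference.** Section 6.2 uses a 96-hour window for time to first detection. If the proportions shared that window, accurate ONT could lead because culture identification averaged 4.8 days in the pilot. The text does not say that they do. If so, the comparison would mix speed with over-calling and be no easier to interpret.

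What remains after these points is the missing reference standard and the conflict between 6.1 and the pilot statements.

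**Conclusion.** The concern holds for the detection comparison. As written, 6.1 and 6.2 score any counted ONT-positive, culture-negative patient in favour of ONT and offer no way to confirm or discount the call. The planned 77% requires about half of culture-negative patients to be in that group, whereas 1.1 and 1.4 together imply ONT positivity of about 55%. These passages must be reconciled.

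The size of the effect depends on an unknown over-call rate: about 8% of trials would favour ONT at f = 10%, 20% at f = 20%, 39% at f = 30%, 62% at f = 40% and 82% at f = 50%. This assumes a two-sided uncorrected chi-square test, 70 per arm, patient-level detection and no culture-positive patient missed. With Fisher's test the last figure is 78%; with 90% sensitivity and chi-square it is 58%.

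It does not follow that ONT over-calls, or that the trial's success criteria would be met through over-calling. The conclusion is that a higher ONT-positive proportion, taken alone, is evidence of neither better detection nor better stewardship.

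**What to change.** In 6.2, make agreement of ONT with final standard culture in Arm 2 the detection analysis: positive and negative percent agreement, at patient level and for each Table 2 organism, with exact 95% intervals. Report ONT-only calls separately as unconfirmed, cross-checked against later surgical-site and abdominal-fluid cultures. Keep the between-arm proportions as descriptive only, define which organisms count and which test defines detection in Arm 2, and state that a higher ONT-positive proportion alone will not be read as improved detection or stewardship.

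In 6.1, remove the stewardship label from 54% v 77% and reconcile the 77% with 1.1 and 1.4.

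The agreement analysis needs plan wording and a cross-tabulation of results that 5.3 already captures. There are three costs. The detection claim becomes less favourable. Some organisms that are truly present but do not grow in culture will be labelled unconfirmed. And 6.1 must say openly that 140 was derived from a positivity difference and not from the antibiotic-use endpoint.

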1.5 Study Rationale and Risk Analysis (Risks to Benefits Ratio)

1.5.1 Study Rationale

SSIs are one of the most common and costly of hospital-acquired infections within the US, accounting for 20% of all hospital-acquired infections¹³. A single SSI increases hospital stay by an average of 9.7 days and accounts for a 2- to 11-fold increase in the risk of mortality¹³. Patients with pancreatic cancer are clinically vulnerable and have a particularly high risk of SSI following pancreatic head resection, with global incidence rates ranging from 25 – 45% of patients undergoing the procedure^{1,2}. The occurrence of a SSI increases the rate of mortality and the need for additional invasive procedures, and it can result in delay or failure to complete adjuvant chemotherapy^{9,58}.

Rapid etiologic diagnosis of biliary microbial contamination can facilitate timely and rational post-operative antimicrobial therapy, reducing the risk of a SSI developing. SCs, however, can take many days to return actionable results^{36,37} and are typically received over the course of 4-7 days. Bile cultures are often polymicrobial, a mixture of anaerobic and aerobic species, carry multiple antibiotic resistant phenotypes, and contain fungal species³⁸⁻⁴¹. This contributes towards delays in timely results, and the temporal separation between the initial broad-spectrum treatment and the acquisition of all the diagnostic information often results in uncertainty and the administration of multiple empiric antimicrobials⁴².

Next-generation sequencing platforms, such as Illumina and ION Torrent, have been widely used in the identification and characterization of microbial species, including previous characterization of the bile microbiome in healthy and diseased states^{59,60}. However, in practice, these technologies require at least 16 hours for the sequencing run alone and analysis of the sequencing data can only be performed once the sequence run has concluded^{47,61}.

ONT sequencing has been demonstrated to successfully characterize microbial populations present in a range of clinical samples and situations in as little as 6 hours^{42,46,47,62-77}. Moreover, we have previously demonstrated that ONT sequencing provides a rapid, comprehensive, and accurate profile of microbial pathogens and antibiotic resistance phenotypes present in intraoperative bile aspirates matching SC techniques^{44,48}. Collectively, this suggests that the incidence rate of SSIs occurring in patients undergoing pancreatic head resection may potentially be reduced by the use of ONT sequencing to rapidly characterize intraoperative biliary microbial contamination and guide early targeted antimicrobial therapy post-surgery, more rapidly than SCs. Additionally, use of ONT sequencing would improve antibiotic stewardship by reducing the use of broad-spectrum antibiotics, and patients would benefit either by receiving a more targeted antimicrobial approach or by being taken off unnecessary broad-spectrum antibiotics earlier which currently is not possible, subsequently reducing the

risk of clinically relevant antibiotic-associated adverse events. Clinical risk to the patient is minimal.

